2.4.6 Analyses of pharmacokinetic and pharmacodynamic variables

N/A.

2.4.7 Analyses of patient reported outcome variables

The data originally planned were no longer considered to be critical and evaluations will not be performed.

2.5 DATA HANDLING CONVENTIONS

2.5.1 General conventions

The following formulas will be used for computation of parameters.

HbA1c

The formula to convert HbA1c from Diabetes Control and Complications Trial (DCCT) aligned value to International Federation of Clinical Chemistry and Laboratory Medicine (IFCC) standardized value is,

$$\text{IFCC-HbA1c (mmol/mol)} = [\text{DCCT-HbA1c (\%)} - 2.15] \times 10.929.$$

Renal function formulas

The estimated GFR (mL/min/1.73 m²) will be calculated using the 4 variable Modification of Diet in Renal Disease (MDRD) formula:

Standard unit: $eGFR \text{ (mL/min/1.73 m}^2\text{)} = 175 \times [\text{Serum Creatinine } (\mu\text{mol/L)/88.4}]^{-1.154} \times \text{Age (year)}^{-0.203} \times 1.212 \text{ (if Black)} \times 0.742 \text{ (if Female)}$

Conventional unit: $eGFR \text{ (mL/min/1.73 m}^2\text{)} = 175 \times \text{Serum Creatinine (mg/dL)}^{-1.154} \times \text{Age (year)}^{-0.203} \times 1.212 \text{ (if Black)} \times 0.742 \text{ (if Female)}$

2.5.2 Missing data

For categorical variables, patients with missing data are not included in calculations of percentages unless otherwise specified. When relevant, the number of patients with missing data is presented.

Derived variables will be considered missing if any of the original variables required to calculate them are missing. For example, if either a baseline assessment or an endpoint assessment is missing for a particular patient, then change from baseline at endpoint will be missing. Depending upon the assessment, analyses may not include all patients in the analysis population, because certain patients in the intended population may have missing data.

Incomplete date of first administration of IMP

Date/time of first administration is the first non-missing start date/time of IMP.

For patients who are randomized and dispensed a treatment kit but who are lost to follow-up just after Visit 2, the date of first administration will be imputed using the date of randomization. When a patient is randomized but not exposed, “Not taken” should be ticked in the e-CRF “First dose IMP” module.

Handling of computation of treatment duration if IMP end of treatment date is missing

For the calculation of the treatment duration, the date of the last dose of IMP is equal to the date of last administration reported on the e-CRF “Treatment status library” page. If this date is missing, the exposure duration should be left as missing.

The last dose administration should be clearly identified in the case report form and should not be approximated by the last returned package date.

In the case of subjects being exposed to more than 1 IMPs, the missing end of treatment date for one IMP could be imputed as the day before the non-missing first administration date of the next IMP date.

Handling of medication missing/partial dates

No imputation of medication start/end dates or times will be performed. If a medication date or time is missing or partially missing and it cannot be determined whether it was taken prior or concomitantly, it will be considered a prior, concomitant, and post-treatment medication.

Handling of adverse events/hypoglycemia with missing or partial date/time of onset

Missing or partial adverse event/hypoglycemia onset dates and times will be imputed so that if the partial adverse event/hypoglycemia onset date/time information does not indicate that the adverse event/hypoglycemia started prior to treatment or after the treatment-emergent adverse event period, the adverse event/hypoglycemia will be classified as treatment-emergent. No imputation of adverse event end dates/times will be performed. These data imputations are for categorization purpose only and will not be used in listings. No imputation is planned for date/time of adverse event resolution.

Handling of adverse events/hypoglycemia when date and time of first IMP administration is missing

When the date and time of the first IMP administration is missing, the day of randomization should be considered as the start date of TEAE period (see [Section 2.1.4](#)). The exposure duration should be kept as missing.

Handling of adverse events/hypoglycemia when IMP end of treatment date is missing

For the purpose of defining TEAE period, the date of the last administration of IMP is equal to the date of the last administration reported on the eCRF “Treatment Status Library” page.

If the date of last administration reported on the eCRF “Treatment Status Library” page is

- Partially missing, it will be imputed with a date as late as possible before or on the date of last available information on eCRF “Completion of End of Study/Follow-up”.
- Completely missing, it will be imputed with the date of last available information on eCRF “Completion of End of Study/Follow-up” page.

If the date of last available information on eCRF “Completion of End of Study/Follow-up” page is

- Partially missing, it will be imputed with a date as late as possible.
- Completely missing, all adverse events occurred on or after the first administration of IMP will be considered as treatment emergent adverse events.

Handling of missing assessment of relationship of adverse events to IMP

If the assessment of the relationship to IMP is missing, the relationship to IMP has to be assumed and the adverse event considered as such in the frequency tables of possibly related adverse events, but no imputation should be done at the data level.

Handling of missing severity/grades of adverse events

If the severity/grade is missing for 1 of the treatment-emergent occurrences of an adverse event, the maximal severity on the remaining occurrences will be considered. If the severity is missing for all the occurrences, a “missing” category will be added in the summary table.

Handling of potentially clinically significant abnormalities

If a patient has a missing baseline he will be grouped in the category “normal/missing at baseline.”

For PCSAs with 2 conditions, one based on a change from baseline value or a normal range and the other on a threshold value, with the first condition being missing, the PCSA will be based only on the second condition.

For a PCSA defined on a threshold and/or a normal range, this PCSA will be derived using this threshold if the normal range is missing; e.g., for eosinophils the PCSA is > 0.5 GIGA/L or $>ULN$ if $ULN \geq 0.5$ GIGA/L. When ULN is missing, the value 0.5 should be used.

Measurements flagged as invalid by the laboratory will not be summarized or taken into account in the computation of PCSA values.

Linked adverse events that worsened or became serious

An AE that worsened or became serious will have a separate record in the data from the original event record with an AE identification number that links the new record to the original record. An AE that worsened or became serious will be considered a new recurring AE in the summary of recurrent events or in the summary of events by time intervals.

Handling of missing data for continuous efficacy endpoints

Please see [Section 2.4.4.1](#) and [Section 2.5.3](#).

2.5.3 Windows for time points

The following steps will decide how the scheduled and/or unscheduled visits will be used in the analyses on efficacy variables and the by-visit summaries for safety variables.

Step 1 A scheduled measurement will be used if it is available; otherwise, an unscheduled measurement (including the end of treatment/study visit for those prematurely discontinued) will be used if it happens to be on the same date as the date of the scheduled visit.

Step 2 After Step 1, if there are still no measurement for a given parameter at a scheduled visit, the analysis window below ([Table 4](#)) will be applied to re-allocate a post-baseline unscheduled measurement to a scheduled measurement.

Table 4 - Analyses window definition

Scheduled visit post baseline	Targeted study day	Analysis window in study days
Week 6 (Visit 6)	42	1 to 83
Week 12 (Visit 14)	84	84 to 104
Week 18 (Visit 16)	126	105 to 153
Week 26 (Visit 19)	182	154 to 195

Study days are calculated from the day of first administration of IMP; the day of first administration of IMP (or the day of randomization if not exposed) is Day 1.

After applying the above time windows, if multiple assessments are associated to the same time point, the closest from the targeted study day will be used. In case of equality, the last measurement will be used. Re-allocated scheduled visits (i.e., visit numbers) should be sequential if ordered by the date of measurement.

After Step 2, if there are still no measurement for a given parameter at a scheduled visit, data is considered missing for efficacy analyses, where multiple imputation would be applied as appropriately as described in [Section 2.4.4](#).

For endpoints where measurements were only taken at baseline and Week 26, post-baseline measurement that is closest to the Week 26 target day will be used for Week 26.

Reference day

The reference day for the calculation of extent of exposure, time to onset, and relative days will be the day of the first administration of IMP or the day of randomization if not exposed to IMP, denoted as Day 1.

Baseline definition for efficacy/safety data

For the safety analyses, the baseline for a given parameter is defined as the last available measurement including unscheduled assessments, assessed prior to the first administration of IMP. For the efficacy analyses, the baseline for a given parameter is defined as the last available measurement including unscheduled assessments, assessed prior to the first administration of IMP or the last available value before randomization if not treated with IMP.

Summary statistics by visit for continuous efficacy endpoints

Summary statistics (number, mean, SD, SE, minimum, median, maximum) of continuous efficacy endpoints (observed data and change from baseline) will be provided at scheduled visits as per protocol. Summaries showing data by visit will be presented according to the visit number (or re-allocated visit number) and labeled with the targeted approximate day/week.

Last on-treatment value for laboratory variables and vital signs

The last on-treatment value is the final measurement assessed during the treatment epoch, regardless of the introduction of rescue therapy, including measurements at unscheduled visits.

Display of safety data by visit (laboratory variables and vital signs)

Descriptive statistics (number, mean, SD, minimum, median, maximum) of quantitative laboratory variables and vital signs (observed data and change from baseline) during the TEAE period will be provided at scheduled visits. In addition, these summaries will also include a row for the 'last value on-treatment' to describe the last available on-treatment value (see above). Summaries showing data by visit will be presented according to the visit number (or re-allocated visit number) and labeled with the targeted approximate day/week.

As specified in the study protocol, laboratory data from scheduled visits are reported by central laboratories. The local results will not be used in the efficacy analyses or in the definition of baseline for both safety and efficacy analyses. In the safety analyses, local results will only be used in the PCSA summary if they are accompanied by a local laboratory normal range.

When a patient has more than 1 measurement from the central laboratory for the same laboratory parameter on the same date, the average of the measurements will be used. For the same laboratory parameter, if a patient has more than 1 measurement on different dates for the same scheduled visit, the value closest to the date of the visit will be used for the scheduled visit. When the values for the same scheduled visit are equidistant, the last value should be used for the scheduled visit. Similar rules will be applicable to a patient who has more than 1 set of measurements for the same vital sign parameter (i.e., SBP, DBP, or HR) on the same date.

26-week randomized treatment period

The 26-week randomized treatment period is the time from first administration of IMP to the last administration of IMP on or before Visit 19/Week 26 (or Day 182 if Visit 19/Week 26 date is missing). This is for defining EOT status at Week 26 and analyzing selected efficacy parameters during the 26-week randomized core treatment period.

TEAE period for the 26-week randomized treatment period

The TEAE period for 26-week randomized treatment period is (1) the time from the first administration of the IMP up to 10 days (1 day for hypoglycemia) after the last administration of IMP if the patient discontinued treatment on or before Visit 19/Week 26 (or Day 182 if Visit 19/Week 26 date is missing), or (2) the time from the first administration of the IMP to the administration at Visit 19/Week 26 (or Day 182 if Visit 19/Week 26 date is missing) if the patient remained treated beyond Visit 19/Week 26. This is for the purpose of safety analyses during the 26-week randomized treatment period.

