2.1.3.1 Primary efficacy endpoint(s)

The primary efficacy endpoint is the change from baseline to Week 26 in HbA1c (%).

Blood samples for HbA1c measurements will be collected at Screening and at study time points listed in study flow chart and will be measured at a central laboratory.

If a patient needs to receive rescue antidiabetic medication or if a decision to permanently discontinue the IMP is made, an assessment of HbA1c should be performed before the introduction of rescue medication/permanent discontinuation. Following introduction of rescue medication, the patient should continue in the study and all study procedures according to the protocol should be performed.

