2.4.4.2 Analyses of secondary efficacy endpoints

Analyses of the secondary efficacy endpoints will be performed using the ITT population for all patients and, separately, by ethnicity/race subgroup. The originally collected change from baseline to Week 26 in 2-hour glucose excursion will no longer be considered critical and will not be analyzed.

For all continuous secondary endpoints except 2-hour glucose excursion, summary statistics at scheduled visits and the changes from baseline will be provided using observed cases for each treatment group, both for the overall population and separately for each ethnicity/race subgroup. The summary will include the number of observations, mean, SD, SE, minimum, median, and maximum. Graphical presentations will also be used to examine trends over time using mean values (\pm SE) and mean changes from Baseline (\pm SE) at each of the scheduled visits. For percentage (%) of patients achieving the HbA1c target of <7% at scheduled visits, the proportion in each treatment group will be provided. All values at scheduled visits will be used to determine whether a patient is a responder or not, even if they are measured after IMP discontinuation or introduction or rescue therapy. If no assessment is available at scheduled visits, patients will be treated as failures (non-responders).

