2.4.4.4 Additional efficacy analysis

Analyses of other efficacy endpoints will be performed on the ITT population using all assessments obtained during the 26-week randomized treatment period, including those obtained after IMP discontinuation or introduction of rescue therapy. Descriptive statistics will be summarized by treatment group, both for the overall population and separately for each ethnicity/race subgroup.

All other efficacy variables originally collected, except the change from baseline to Week 12 in HbA1c and percentage of patients requiring rescue therapy by Week 26, will no longer be considered critical and will not be analyzed. The analysis of other endpoints (see [Section 2.1.3.3](#)) will be descriptive with no formal testing.

The number (%) of patients who used rescue therapy and a KM curve for the time to first rescue therapy will be provided by treatment group. A list of patients who used rescue therapy will also be provided. Time to rescue will be defined as the number of days from the first administration of IMP until the start date of any rescue medication. Patients who did not take any rescue medication

during the 26-week treatment period will be considered as censored observations. The censoring time will be the last administration date (e-CRF “Treatment Status Library” page), or the end date of the study (e-CRF “Completion of End of Study/Follow-up” page) if the last administration date is not available, or the last contact date if the last administration date and end date of the study are not available.

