Appendix C Study flow chart

STUDY FLOW CHART

Study Period	Screening		Open-label Randomized Treatment																	Follow-Up Visit	
	1	1.2 ^b	2	3	4	5	6	7	8	9	10	11	12	13	14	15	16	17	18	19 ^c	19 + 3
VISIT ^a				☎	☎	☎	☎	☎		☎	☎	☎	☎	☎		☎		☎	☎		☎
WEEK	-2	-1	0	1	2	3	4	5	6	7	8	9	10	11	12	15	18	21	24	26	26+3 days
Inclusion criteria including Informed Consent ^d	x		x																		
Exclusion criteria	x		x																		
Patient demography	x																				
Medical/surgical history (including diabetes)	x																				
Prior medication history	x	x																			
Physical examination	x																				
Height	x																				
Body weight and BMI ^e	x		x												x		x				x
Vital signs ^f	x		x						x						x		x				x
Diet and lifestyle counseling ^g	x		x						x						x		x				x
IRT contact ^h	x		x						x						x		x				x
Randomization			x																		
Dispensation of IMP (as appropriate)			x						x						x		x				
Pen-injector and self-injection training and re-training ⁱ			x	x	x	x	x	x	x	x	x	x	x	x	x	x	x	x	x		

Study Period	Screening		Open-label Randomized Treatment																	Follow-Up Visit	
	1	1.2 ^b	2	3	4	5	6	7	8	9	10	11	12	13	14	15	16	17	18	19 ^c	19 + 3
VISIT ^a				☎	☎	☎	☎	☎		☎	☎	☎	☎	☎		☎		☎	☎		☎
WEEK	-2	-1	0	1	2	3	4	5	6	7	8	9	10	11	12	15	18	21	24	26	26+3 days
Review and evaluation/adjustment of IMP doses			x	x	x	x	x	x	x	x	x	x	x	x	x	x	x	x	x	x	
Collection of used and unused IMP pens; compliance check									x						x		x			x	
Glucometer/supplies/diary dispensation			x																		
Glucometers, SMPG, hypoglycemia, insulin dose titration, diary training and re-training ⁱ			x	x	x	x	x	x	x	x	x	x	x	x	x	x	x	x	x		
SMPG ^j			x	x	x	x	x	x	x	x	x	x	x	x	x	x	x	x	x	x	
Two-hour standardized meal test (a sub-set of patients only)		x																		x	
HbA1c (central laboratory)	x														x		x			x	
FPG (central laboratory) (A 1-time repeat measurement before Visit 2 is permitted)	x														x					x	
PRO questionnaires ^k			x												x					x	
Hematology ^l	x																				
Serum chemistry ^m	x																				
Urinalysis ⁿ	x																				
eGFR ^o	x																				
Amylase, Lipase	x																				
Serum calcitonin			x																		
Pregnancy test ^p	x		x												x		x			x	
Concomitant medications	Continuously assessed and recorded throughout the study																				

Study Period	Screening		Open-label Randomized Treatment																	Follow-Up Visit	

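### Table 4 opens the Week 12 window on its own target day, so unscheduled HbA1c values from Days 63–83 cannot count at Week 12; the Week 6 row also carries the wrong visit number

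*SAP*

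**What the plan says.** SAP section 2.5.3 fills a scheduled visit in two steps. Step 1 takes the scheduled measurement. Failing that, it takes "an unscheduled measurement (including the end of treatment/study visit for those prematurely discontinued"), but only if that measurement falls on the date of the scheduled visit. In Step 2, if the visit is still empty, Table 4 "will be applied to re-allocate a post-baseline unscheduled measurement to a scheduled measurement". Only after that, "if multiple assessments are associated to the same time point, the closest from the targeted study day will be used". A visit still empty after Step 2 is missing for efficacy.

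Table 4 gives:

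- Week 6 (labelled Visit 6): target Day 42, window 1–83
- Week 12 (Visit 14): target Day 84, window 84–104
- Week 18 (Visit 16): target Day 126, window 105–153
- Week 26 (Visit 19): target Day 182, window 154–195

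The same section says that summaries of continuous efficacy endpoints "will be provided at scheduled visits as per protocol". In the Appendix C flow chart, the row "HbA1c (central laboratory") is marked at screening and at Weeks 12, 18 and 26, not at Week 6.

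Section 2.4.4.4 drops the other efficacy variables "except the change from baseline to Week 12 in HbA1c and percentage of patients requiring rescue therapy by Week 26". For the HbA1c <7% proportion, section 2.4.4.2 says: "If no assessment is available at scheduled visits, patients will be treated as failures (non-responders").

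**The concern.** The Week 12 window accepts nothing before its target, while the next two windows accept values three and four weeks early. The SAP gives no reason for the difference. A Day 83 value is one day from the Week 12 target and 41 days from the Week 6 target, yet it goes to Week 6.

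Such values are foreseen. Section 2.1.3.1 says that "an assessment of HbA1c should be performed before the introduction of rescue medication/permanent discontinuation", and Step 1 names the end-of-treatment or end-of-study visit as a source of unscheduled values.

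Two Week 12 results are at stake: the HbA1c change, which is one of only two other efficacy endpoints still analysed, and the by-visit HbA1c <7% proportion, where a missing value is a failure. A patient who leaves on Day 80 with an HbA1c below 7% and no Visit 14 sample is missing from the former and a non-responder in the latter.

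**Working it through.** **Window limits.** The inputs are the targets and windows in Table 4. The limits for Weeks 18 and 26 are reproduced exactly by taking the midpoint of adjacent targets and giving the midpoint day to the later visit. The limit for Week 12 is not.

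| Visit | Target | Window | Midpoint with previous target | Days accepted before / after target |
|---|---|---|---|---|
| Week 12 | 84 | 84–104 | (42 + 84)/2 = 63 | 0 / 20 |
| Week 18 | 126 | 105–153 | (84 + 126)/2 = 105 | 21 / 27 |
| Week 26 | 182 | 154–195 | (126 + 182)/2 = 154 | 28 / 13 |

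Two other rules were tried for Week 12. Giving the midpoint day to the earlier visit opens the window on Day 64. Taking the midpoint of Day 1 and Day 84, because HbA1c has no Week 6 visit, gives 42.5 and so Day 43. Neither gives Day 84.

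**Days affected.** Days 64 to 83 are strictly nearer Day 84 than Day 42: 83 − 64 + 1 = 20 days. Day 63 is 21 days from each target, and the table's handling of Days 105 and 154 gives such a tie to the later visit, so 21 days in all. The Week 12 window is 104 − 84 + 1 = 21 days wide; on the table's own pattern it would be 104 − 63 + 1 = 42.

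**Can another rule recover the value?** No. Step 1 needs the same date as the scheduled visit, and the closest-to-target rule acts only after the windows have been applied. By contrast, a patient leaving the same four days before a later target keeps the value: Day 126 − 4 = 122 lies in 105–153, and Day 182 − 4 = 178 lies in 154–195.

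**Size.** The SAP does not say how many patients are affected. Assume that 5%, 10% or 20% of 120 patients per arm leave evenly over 182 days, each with a final HbA1c. The expected number leaving on Days 63–83 is 120 × rate × 21/182:

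- 5%: 0.69 patients, or 0.58 percentage points of 120
- 10%: 1.38 patients, or 1.15 points
- 20%: 2.77 patients, or 2.31 points

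The point figures are upper limits that apply only if every lost value was below 7%. One patient is 1/120 = 0.83 points in a full arm, or 1/40 = 2.5 points in an assumed subgroup arm of 40.

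**Visit label.** Aligning the visit and week rows of Appendix C gives Visit 6 = Week 4, Visit 8 = Week 6, Visit 14 = Week 12, Visit 16 = Week 18 and Visit 19 = Week 26. Three of the four Table 4 labels agree; Week 6 as Visit 6 does not.

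**The case against.** The SAP never states a midpoint rule; it is inferred from two boundaries. The windows are contiguous and do not overlap, and the Week 6 window is symmetric about Day 42 (41 days each side), which may be how Day 83 arose. This stands as far as it goes: the document cannot prove a slip. It also gives no reason for treating Week 12 differently. The lack of a Week 6 HbA1c would argue for an earlier Week 12 opening, not for opening on the target.

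It can also be said that the value is not lost altogether, because sections 2.5.3 and 2.5.4 allow summaries by re-allocated visit, so a Day 70 HbA1c might be shown at Week 6. Step 2, however, fills a gap for a parameter at a scheduled visit, and HbA1c has none at Week 6. The natural reading is that the value counts nowhere. On either reading it does not count at Week 12.

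The reach is narrow, and that stands in full. Patients who start rescue or stop the study drug are meant to stay for all visits, so most should have a Visit 14 sample. A Visit 14 sample taken early is kept by Step 1. Local laboratory results are excluded from efficacy in any case. What remains is mainly patients who leave the study on about Days 63–83 with a central HbA1c, plus any who stay but miss Visit 14. All efficacy analysis is descriptive, and the HbA1c <7% secondary endpoint is defined at Week 26.

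Finally, Day 63 is not the only possible opening for HbA1c, since Day 43 can also be argued. Day 63 has the merit of following the table's own pattern and giving Week 12 the same 21 days before target as Week 18.

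**Conclusion.** The point holds. Table 4 breaks its own pattern at Week 12, and applied as written it excludes usable HbA1c values from the Week 12 change and counts those patients as Week 12 non-responders. The Week 6 visit number contradicts Appendix C.

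The window limits and the label follow directly from the SAP. The number of patients does not: 0.7 to 2.8 per arm rests on the assumed 5% to 20% withdrawal, its even spread, and a final HbA1c for every patient who leaves. Week 26 results, including the primary endpoint, are not affected. This is a small defect that should be corrected before database lock.

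**What to change.** In Table 4, change two rows:

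- Week 6 (Visit 8): target Day 42, window 1 to 62
- Week 12 (Visit 14): target Day 84, window 63 to 104

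Add one sentence stating that the Week 6 row applies only to parameters that Appendix C schedules at Week 6. Under this text an unscheduled HbA1c from Days 1–62 is not assigned to any visit; the sentence should say so, so that this is a stated choice.

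The cost is two window limits, one visit number and one sentence. Values taken at scheduled visits and all Week 26 results stay as they are. If Day 84 was intended, the SAP should give the reason and still correct the visit number.
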